#### 15.2.4. EXPLORATORY MEASURES ANALYSIS

##### Time to cecum

Net duration from insertion of the colonoscope to visualization of the cecum will be summarized a table by the following time categories:

- ≤10 min
- 11-20 min
- 21-30 min
- ≥31 min

Count and percentage will be provided for time category.

In addition a descriptive statistics for continuance variable, including number of subjects, mean, median, standard deviation, minimum, and maximum will be provided..

Start & end time of any diagnostic or therapeutic intervention which will be performed during the insertion phase, will be calculated and reduced from the total time to Cecum.

##### Total examination time

Net duration from insertion of the colonoscope removing of the whole instrument (Guide: >6min withdrawal time) will be summarized in a table by the following time categories:

- ≤30 min
- 31-40 min
- 41-50 min
- ≥51 min

The analysis will include only procedures that were completed to the cecum.

Count and percentage will be provided for time category.

In addition a descriptive statistics for continuance variable, including number of subjects, mean, median, standard deviation, minimum, and maximum will be provided.

Start & end time of any diagnostic or therapeutic intervention which will be performed during the procedure, will be calculated and reduced from the total time to Cecum.

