### 7.3. EXPLORATORY ENDPOINTS

1. Net time until cecum is visualized
2. Net time of the entire colonoscopy procedure
3. Rate of procedures where the cecum was visualized .
4. User satisfaction will be evaluated by a questionnaire filled-in by the physicians and nurses who conduct the procedures and assemble the MCS.

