### **14.3. PROCEDURE AND CECUM REACHED TIME**

Time to cecum is defined as the net duration from insertion of the colonoscope to visualization of the cecum.

Time of the whole procedure is defined as the net duration from insertion of the colonoscope until removing of the whole instrument (guide: >6min withdrawal time).

Start & end time of any diagnostic or therapeutic intervention which will be performed during the insertion or retrograde phase, will be calculated and reduced from the total time.

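### Under 'Total examination time' (15.2.4), intervention time is subtracted from the time to cecum instead of the total examination time, so followed literally the exploratory net procedure time is not net

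*Combined protocol and SAP*

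**What the plan says.** The protocol names two exploratory time endpoints in section 7.3: item 1, "Net time until cecum is visualized", and item 2, "Net time of the entire colonoscopy procedure". Three places then govern how intervention time is removed.

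- **Section 14.3** defines both quantities as net: "Time to cecum is defined as the net duration from insertion of the colonoscope to visualization of the cecum" and "Time of the whole procedure is defined as the net duration from insertion of the colonoscope until removing of the whole instrument". Its subtraction rule covers interventions "performed during the insertion or retrograde phase, will be calculated and reduced from the total time".
- **Section 15.2.4, 'Time to cecum'**, covers interventions "performed during the insertion phase, will be calculated and reduced from the total time to Cecum".
- **Section 15.2.4, 'Total examination time'**, introduces its measure as "Net duration from insertion of the colonoscope removing of the whole instrument", restricts the summary to procedures completed to the cecum, and sets bands of ≤30, 31-40, 41-50 and ≥51 minutes. Its closing sentence covers interventions "performed during the procedure, will be calculated and reduced from the total time to Cecum".

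**The concern.** The closing sentence sits under the total-time heading and counts interventions from the whole procedure, but it deducts them from a different endpoint. No other sentence in that paragraph deducts anything from the total examination time. A programmer working from 15.2.4 alone would have an instruction that can be executed and that leaves the reported total time gross.

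Procedure time has some bearing on the device. Section 4.7 acknowledges that cleansing may lengthen the procedure by some minutes, and section 4.1 expects polyp removal and biopsies where needed. If intervention time stays in the total, the summary mixes time spent on therapy with time attributable to insertion, cleansing and inspection. The netting is there to keep these apart.

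**Working it through.** The plan states no figure to reproduce here. The check sets the rules side by side and then follows each one through.

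**Notation.** For one subject, in minutes:
- C = gross time from insertion to cecum
- T = gross time from insertion to removal of the instrument
- I = intervention time during insertion
- W = intervention time during withdrawal

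**Rules as written.**

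| Place | Interventions counted | Quantity reduced | Result |
|---|---|---|---|
| 14.3 | insertion and withdrawal | total time | T − I − W |
| 15.2.4, Time to cecum | insertion only | time to cecum | C − I |
| 15.2.4, Total examination time | whole procedure | time to cecum | T left unreduced |

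The first two rows fit together. Insertion-phase interventions fall inside the interval to the cecum, so only they can be removed from it. Withdrawal-phase interventions fall outside that interval, so the total in 14.3 can only be the whole-procedure time. The third row conflicts with 14.3 and with the net duration in its own opening line.

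**Error in total time under the literal reading.** Reported minus intended = T − (T − I − W) = I + W. It is zero for a subject with no intervention and positive otherwise. The mean over analysed subjects is therefore too long by the mean of I + W.

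**Size.** The documents give no procedure or intervention durations. The minutes below are assumptions, chosen to show a range.

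| T | I | W | Intended T − I − W | Literal T | Excess | Band, intended → literal |
|---|---|---|---|---|---|---|
| 40 | 0 | 0 | 40 | 40 | 0 | 31-40 → 31-40 |
| 38 | 0 | 3 | 35 | 38 | 3 | 31-40 → 31-40 |
| 40 | 0 | 5 | 35 | 40 | 5 | 31-40 → 31-40 |
| 40 | 0 | 10 | 30 | 40 | 10 | ≤30 → 31-40 |
| 40 | 2 | 10 | 28 | 40 | 12 | ≤30 → 31-40 |
| 52 | 2 | 12 | 38 | 52 | 14 | 31-40 → ≥51 |

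The direction of the error does not depend on these inputs. Whether a band changes does: the short interventions shown move the continuous summaries only, and the longer ones move the subject by one or two bands.

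**The case against.** The strongest reply is that this is an editing slip whose intent is clear. The sentence repeats the closing sentence of the time-to-cecum paragraph with the phase changed and the reference to the cecum left in. The word net appears in the objectives (6.3), in the endpoints (7.3), in 14.3 and at the head of the paragraph itself. On that view, 14.3 already supplies a correct netting rule for total time, and reporting gross time would breach several consistent statements. This is fair as to intent, and it keeps the point small. It does not remove the point, because the sentence is current analysis text, can be carried out as written, and contradicts 14.3.

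A reader might go further and infer that both time endpoints come out wrong, with time to cecum shortened by W. With an assumed C = 12, I = 0 and W = 15, it would be 12 − 0 − 15 = −3 minutes, which is impossible. The documents do not support that as the expected outcome. Time to cecum has its own heading and its own rule, limited to insertion-phase interventions, and that rule gives C − I = 12 in the same example. The distortion arises only if an analyst takes the sentence from the total-time paragraph and applies it over, or on top of, the rule meant for time to cecum. An impossible value would also be likely to prompt a query.

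**Conclusion.** The point stands as a minor error. The subtraction sentence under 'Total examination time' names the wrong quantity. Followed literally, it leaves endpoint 7.3, item 2, too long by I + W in every subject with an intervention. The conclusion about direction rests only on the text. The size rests on intervention durations that the documents do not give: from no change, through a shift in the continuous summaries alone, to a change of one or two bands in the assumed examples.

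Time to cecum is correctly governed as the plan stands, subject to the misapplication described above. The affected endpoint is exploratory and summarised descriptively, with no hypothesis or threshold attached. The primary analysis and the sample size are unaffected.

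**What to change.** In the closing sentence of 'Total examination time' in 15.2.4, change the quantity reduced, so that intervention time is *subtracted from the total examination time*. This matches 14.3 and gives T − I − W. Leave the time-to-cecum paragraph as it is, giving C − I. The cost is one phrase. No new data are needed, because the plan already relies on the start and end times of each intervention.

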#### Cecal intubation

The count and percentage of subjects for which cecum could be reached by the colonoscope with the MCS will be presented together with 95% confidence intervals.

#### User satisfaction

Will be summarized in a table via descriptive statistics by data type. The questionnaire will be filled in by the physicians who will conduct the procedures and the nurse who assists in the procedure and assembles the MCS and includes their feedback on the system

### **15.3. BLINDING AND RANDOMIZATION**

Blinding and randomization are not applicable in this study.

### **15.4. POOLING**

In addition to generating clinical reports from this study, data from the sites in this multi-center study and possibly from additional studies performed in other clinical centers following the same study design and using a common protocol may be pooled. In such a case the study data may be pooled and subgroup analysis of the primary endpoint by center will be used to evaluate the poolability of the results. The safety and clean rate by center interaction will be tested with appropriate standard statistical methods. Data from the user satisfaction questionnaires may be pooled later as well to be used in a future usability study.

### **15.5. HANDLING OF MISSING DATA**

Dropouts and subjects lost to follow will be treated as missing values and therefore dropped from analysis of performance variables. A subject for whom the procedure was not performed to due to no or partial bowel preparation will not be entered into this analysis. No imputation of missing data will be performed.

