## 7. STUDY ENDPOINTS

### 7.1. PRIMARY ENDPOINTS

The rate of adequate cleansing level per subject will be evaluated by the BBPS scoring index pre- and post the cleansing operation.

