### Colonoscopy procedures

- The procedure will be performed by the clinical investigator(s), experienced in GI endoscopy according to local standard of care. Anesthesia will be applied as well per the standard of care. In order to ensure correct operation of the MCS a Motus GI representative may attend the procedure. Using the MCS, requires specific training with the MCS that will be provided by the sponsor prior to the study. MCS operation is described in the Instruction For Use.
- The MCS will be operated according to section “Operating the MCS workstation” in the IFUs. The colon preparation level for each segment of the colon (Left, Transverse, Right) before the cleansing operation during the insertion phase and post the cleansing operation during withdrawal will be evaluated using the BBPS (Appendix A – Scoring method).
- Once the procedure is completed, relevant data will be recorded on the CRF in addition, findings, diagnosis as well as Physician questionnaire will be recorded/completed.

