#### Follow-up

Fourteen days after the procedure, each subject will be contacted by phone to verify that there has been no change in their well-being following the procedure. Any AE will be documented in the CRF. Before a subject is considered “lost to follow-up”, there must be at least two documented attempts to contact the subject.

The company may have the option to match the diagnostic and therapeutic interventions performed during the study with the pathologic results from the lab when obtained.

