### **13.2. SUBJECT WITHDRAWAL**

Subjects will be withdrawn from the study if one of the following occurs;

- The subject voluntarily discontinues his or her participation in the study.
- Continuation of the course of the study would jeopardize the subject's health and/or welfare (at the discretion of the Investigator)
- There is a concurrent illness (unrelated to treatment) that prevents the subject from complying with the study requirements
- The subject is unwilling or unable to comply with the protocol
- The subject was found to be not-eligible following signature of the Informed Consent Form .

The reasons for the subject's withdrawal from the study must be recorded in the subject's CRF and captured on the Subject Enrollment and Visit Log. All withdrawn subjects having performed the colonoscopy procedure with MCS, will be followed up to 14 days post procedure to verify that there have been no changes in their well-being for the entire period of the study.

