#### 14.1.2. POST PROCEDURE CLEANSING PER SUBJECT

Evaluating the cleansing rate of the MCS while withdrawing colonoscope, post the cleaning procedure, for the entire colon.

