#### 15.2.1. ANALYSIS OF POPULATION

Subjects will be excluded from the efficacy analysis as missing/invalid data by the following:

- Subject withdraws
- Unprepared subjects (not taken the preparation or had a partial bowel preparation)
- System technical failure

Individual listings of withdrawal / failure including descriptive information will be provided.

In addition, in cases of incomplete procedure (i.e., the entire colon is not visualized); the overall BBPS per patient will be evaluated based on the colon segments that were visualized.

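### Sections 15.5 and 15.2.1 drop withdrawn and lost-to-follow-up subjects from the performance analysis whatever the timing, so pre/post BBPS pairs already recorded at Visit 2 can be discarded

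*Combined protocol and SAP*

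**What the plan says.** **The exclusion rules.** Section 15.5 says "Dropouts and subjects lost to follow will be treated as missing values and therefore dropped from analysis of performance variables", and adds "No imputation of missing data will be performed". Section 15.2.1 opens its list with "Subjects will be excluded from the efficacy analysis as missing/invalid data by the following"; the first item is withdrawal of the subject, with nothing about when it happens. The other two items are an unprepared subject and a system technical failure.

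**When the data arise.** Section 7.1 gives the primary endpoint: "The rate of adequate cleansing level per subject will be evaluated by the BBPS", before and after cleansing. Section 12.5 (Colonoscopy procedures) says the preparation level of each segment "before the cleansing operation during the insertion phase and post the cleansing operation during withdrawal will be evaluated using the BBPS". Section 14.1.2 describes the second rating as "Evaluating the cleansing rate of the MCS while withdrawing colonoscope, post the cleaning procedure, for the entire colon". Times and cecal intubation (14.3, 14.4) are properties of the same examination.

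**What follows the procedure.** Section 10 provides telephone calls at 48 hours and 14 days, for well-being and adverse events. Section 13.1 makes study completion depend on the 14-day call. The Follow-up paragraph of 12.5 says that before a subject counts as lost to follow-up "there must be at least two documented attempts to contact the subject"; 13.3 repeats this. Section 13.2 foresees withdrawal after the device has been used: "All withdrawn subjects having performed the colonoscopy procedure with MCS, will be followed up to 14 days post procedure".

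**The concern.** A performance variable is missing when it was not recorded. Sections 15.5 and 15.2.1 instead define missingness by the subject's final study status, and that status depends on calls that collect no performance data. For a subject who withdraws or cannot be traced after the colonoscopy, it is untrue that the performance values are missing.

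Two things are at stake. Observed primary data would be thrown away in a trial with about 33 planned evaluable subjects. A day-0 endpoint would also be made conditional on later events. If leaving the study is related to how the examination went, the analysed subjects are a selected subset, and the post-procedure rate and the 95% confidence interval promised in 15.2.2 describe that subset. The listings of withdrawals in 15.2.1 would show that subjects were removed, but would not put their results back into the estimate.

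**Working it through.** **1. The plan's own figures (15.1).** Inputs: alpha 0.05, power 0.80, proportion switching from inadequate to adequate 0.6, proportion switching the other way 0. Sidedness is not stated. With discordant proportion pd = 0.6 and difference d = 0.6, the McNemar normal approximation is

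n = [z(1−α/2)·√pd + z(power)·√(pd − d²)]² / d²

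Two-sided: [1.960 × 0.7746 + 0.842 × 0.4899]² / 0.36 = 10.35, rounded up to 11, which matches the plan. One-sided gives 7.90, rounded up to 8, which does not.

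The plan takes 11 pairs at each of 3 sites (33), adds 9 learning-curve subjects and 4 for withdrawal, and states 47. The parts sum to 46; 42/0.9 = 46.7 rounds up to 47. The difference does not matter here. The relevant inputs are 33 evaluable subjects and 4 budgeted withdrawals.

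**2. Can a complete pair be deleted?**

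| Event | Section | Relation to BBPS ratings |
|---|---|---|
| Pre-cleansing BBPS | 12.5, 14.1.1 | insertion, Visit 2 |
| Post-cleansing BBPS | 12.5, 14.1.2 | scope withdrawal, Visit 2 |
| 48-hour and 14-day calls | 10, 12.5 | after both ratings |
| Loss to follow-up (at least two documented attempts) | 12.5 Follow-up, 13.3 | set out under the 14-day call |
| Withdrawal after the MCS procedure | 13.2 | after the procedure |

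The last two events trigger exclusion under 15.5 and 15.2.1 although the ratings may already exist. So yes, on the text as it stands.

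**3. Bound on the post-procedure rate.** Assumptions, not given in the documents: all 4 budgeted withdrawals occur after the procedure, and 32 of the 33 analysed are adequate (close to the 96% in 15.1). The share of observed pairs deleted is 4/37 = 10.8%. Intervals are exact (Clopper-Pearson).

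| Case | Adequate / pairs | Rate | 95% CI |
|---|---|---|---|
| As reported under the plan | 32/33 | 97.0% | 84.2–99.9 |
| 4 restored, all adequate | 36/37 | 97.3% | 85.8–99.9 |
| 4 restored, none adequate | 32/37 | 86.5% | 71.2–95.5 |

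With fewer late departures, all inadequate, the shift is smaller: one restored gives 32/34 = 94.1% (80.3–99.3), two give 32/35 = 91.4% (76.9–98.2).

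**4. Power.** At the planned 0.6 it exceeds 0.999 with either 33 or 37 pairs.

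**5. The pre/post test in an extreme case.** Take 12 of 33 adequate before (about 36%) and 32 of 33 after: 20 improve, none worsen. Restore 4 pairs that all went from adequate to inadequate, giving 20 versus 4 discordant pairs. Exact McNemar: p = 2 × (1 + 24 + 276 + 2,024 + 10,626) / 2²⁴ = 25,902 / 16,777,216 = 0.0015. Section 15.2.2 names chi-square or Fisher's exact test; Fisher's test on 16/37 before against 32/37 after gives p = 0.0002. Either way the result stays significant at 0.05.

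**The case against.** **A narrower rule may have been meant.** The sentence stands under missing data, 15.2.1 speaks of missing or invalid data, and 15.2.2 bases the primary assessment on all segments observed during the procedure. Section 15.2.1 even keeps incomplete examinations, scored on the segments seen. This suggests the authors had in mind subjects without BBPS data. That may be so, but the text does not say it: loss to follow-up is described under the post-procedure call, and unprepared subjects have their own sentence in 15.5 and their own item in 15.2.1.

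**Stronger readings that do not stand.**
- A reader might infer that one unanswered call removes a subject. Sections 12.5 and 13.3 require at least two documented attempts first.
- A reader might infer that the rule favours the device. Nothing in the documents links poor cleansing to later loss. Under 12.5, when the cecum is not reached the examination goes on without the MCS and the subject completes the study as planned; under 13.2, subjects withdrawn after the procedure are still followed to 14 days. Selection is possible; its direction is unknown.
- A reader might take 86.5% as a forecast. It requires all 4 withdrawals to be late and all 4 subjects to be inadequate. Without selection, at the planned 96% success rate, four inadequate results have probability 0.04⁴, about 3 in a million. Several grounds for withdrawal in 13.2 can also apply before the procedure.

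These objections limit the size of the point and leave the defect in place.

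**Conclusion.** The point holds as a moderate one. As written, 15.5 and 15.2.1 allow recorded Visit 2 performance data to be discarded because of withdrawal or loss to follow-up after the procedure. What is exposed is the reported post-procedure adequate rate and its interval. Under the stated assumptions the rate with all pairs kept lies between 86.5% and 97.3%, against 97.0% reported. These are bounds; the documents give neither the timing of withdrawals nor any reason to expect a particular direction.

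A reader might go further and conclude that the primary hypothesis is at risk. The documents do not support that: the hypothesis is pre/post improvement with no performance threshold for the post-procedure rate, power is above 0.999 either way, and the test remains significant even in the extreme case above. The safety analysis is also untouched, since 15.2.3 uses all enrolled subjects.

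**What to change.** **Section 15.5.** Replace the sentence on dropouts with wording to this effect:

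> A subject is missing for a performance variable only if that variable was not recorded at Visit 2. Subjects who withdraw or are lost to follow-up after the MCS procedure keep their recorded Visit 2 data in the performance analyses. This is subject to the other stated exclusions (learning-curve subjects, unprepared subjects, system technical failure, subjects found ineligible) and to any withdrawal of consent to the use of data.

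**Section 15.2.1.** Limit the withdrawal item to a subject who withdraws before both the pre- and post-cleansing BBPS are recorded. List subjects found ineligible as a separate item: 13.2 treats them as withdrawn, and exclusion criterion 3 can be met during the colonoscopy itself, so the narrower item would otherwise no longer cover them.

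**Cost.** A few lines of text; no extra subjects, procedures or data, and no change to the sample size. The change should be made before results are known, because in an open-label trial a later decision on whom to drop is open to challenge.

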### **15.6. INTERIM ANALYSIS**

An Interim analysis related to pre-procedure cleansing will be conducted after 10 subjects per site or 50 cases overall, whatever comes first. Interim analysis will primarily assess the subjects' pre-

procedure cleansing in order to ensure enough poorly prepped cases for the evaluation of the device capabilities. Preparation procedure may be adjusted as per interim results direction.

